Retrospective Evaluation of Prosthetic Complications and Peri-implant Bone Resorption in Implant-Supported Single Unit Fixed Restorations

Study Protocol

Date: 07.04.2023

Department of Prosthetic Dentistry

Afyonkarahisar Health Sciences University, Faculty of Dentistry

Pre-assignment Details

Participants included in the study were later excluded from the analysis due to reasons such as missing data in patient records, the presence of data outside the specified time frame, patients initially thought to meet the study criteria being incorrectly coded, or medical records being in an unsuitable format or unreadable.

Arm/Group Information

This study does not include any specific study or control groups. The research focuses on the follow-up of participants with certain characteristics over a specified time period.

Type of Units Assigned

- **Period(s):** This is a retrospective study following a 12-month period.
Period Title: Overall Study
Started: This study was conducted by including patients 12 months after delivery of the implant-supported restoration. The sample was completed when a total of 100 patients were reached.
Completed: The number of participants at the end of the study is 100.

Baseline Characteristics

- **Arm/Group Information:** There were no separate groups in the study. The study included a 12-month follow-up of participants with implant-supported single-unit restorations.
Arm/Group Title: There were no separate groups in the study.
- **Baseline Analysis Population Information**
Overall Number of Baseline Participants: 100 participants
- **Baseline Measure Information**
Baseline Measure Title
Age: Age, Continuous
Sex/Gender: Female, Male
- **Measure Type:** Count of Participants

- **Measure of Dispersion:** Not Applicable
- **Baseline Measure Data: Not Available.** The study does not have any baseline data, because the data in the study only includes data from participants at the end of the 12-month follow-up.
- **Unit of Measure:** Not Available

Outcome Measures:

- **Outcome Measure Information:** Implant survival and prosthetic complication rate
 - Outcome Measure Type:** Primary
 - Outcome Measure Title:** Implant survival and prosthetic complication rate
 - Outcome Measure Time Frame:** 12 months after delivery of implant-supported restoration
 - Arm/Group Information:** There were no separate groups in the study. The study included a 12-month follow-up of participants with implant-supported single-unit restorations.

Analysis Population Information:

Overall Number of Participants Analyzed: 100 participants

Outcome Measure Data Table

Measure Type: Count of Participants

Measure of Dispersion/Precision: Not Applicable

Outcome Measure Data: The effect of prosthetic, anatomical and surgical parameters on implant survival rate and prosthetic complications

Unit of Measure: Implant survival and prosthetic complications rate

Statistical Test of Hypothesis:

P-Value: p<0.05

Method: Chi-Squared

Adverse Event Information: Since this is a retrospective analysis, adverse events were not evaluated.

Certain Agreements:

- **Are all PIs Employees of Sponsor?** Yes: The principal investigator is an employee of the sponsor

Results Point of Contact:

- **Name or Official Title:** [name]. Assistant Professor at Afyonkarahisar Health Sciences University, Department of Prosthodontics.
- **Organization Name:** Afyonkarahisar Health Sciences University
- **[contact]
- **E-mail:** [contact]

Document Upload Information:

- **Document Type:** Study Protocol with Statistical Analysis Plan (SAP)
- **Document Date:** 07.04.2023

This retrospective study included 100 volunteer patients aged between 30 and 77 who presented at the Department of Prosthetic Dentistry at Afyonkarahisar Health Sciences University Faculty of Dentistry for prosthetic treatment and received a single-unit implant-supported crown. The evaluation of the included patients was conducted during their 12-month follow-up control appointments after prosthetic loading. After obtaining oral and written consent from the patients, demographic data, prosthetic complications related to single-unit fixed implant-supported prostheses, and peri-implant bone loss assessed via radiographic controls were recorded and analyzed. During clinical examinations, the compatibility of the prostheses with adjacent teeth and gingiva, the presence of gingival recession, patient complaints about the prosthesis, and any prosthetic complications were assessed and recorded. Statistical analyses were performed retrospectively after evaluating the collected data.

Ethical Approval for the Study

Since participation in this study was voluntary and conducted with volunteers, it was reviewed by the Clinical Research Ethics Committee of Afyonkarahisar Health Sciences University. The study was unanimously deemed to comply with medical ethical standards (Date: 07.04.2023, Protocol Code: 2023/4). All volunteers signed an informed consent form approved by the ethics committee before participating in the study.

Volunteer Selection

This study included 100 volunteer patients who applied to the Department of Prosthetic Dentistry at Afyonkarahisar Health Sciences University Faculty of Dentistry for prosthetic treatment and received a single-unit implant-supported crown. Patients were selected from archives and evaluated during their 12-month follow-up appointments through clinical and radiographic examinations. To determine the number of volunteers needed for the study, a sample size calculation was performed using *GPower software* (*GPower* Ver. 3.0.10, Franz Faul, University of Kiel, Germany). With a significance level of $\alpha=0.05$ (95% confidence interval), an effect size (d) of 0.5, and power ($1-\beta$) = 0.80, at least 80 patients were required. To account for potential dropout and data loss during follow-up, an additional 25% (20) patients were added, resulting in 100 patients at the start of the study.

Systemic and dental anamneses of the volunteers were thoroughly evaluated, and inclusion and exclusion criteria were established. Patients meeting the inclusion criteria were provided detailed information about the study plan before the start. Those who agreed to participate signed the

Inclusion Criteria

1. Patients who had received single-unit dental implant treatment and had 12 months elapsed since prosthetic loading.
2. Patients aged 18 and older, regardless of gender.
3. Patients with no systemic health issues.
4. Non-smokers.
5. Patients for whom radiographic bone loss, mobility, and prosthetic complications data were recorded and evaluated.
6. Patients who signed the informed consent form voluntarily after being fully informed about the study's purpose, duration, and requirements.

Exclusion Criteria

1. Patients diagnosed with osteoporosis and/or undergoing bisphosphonate treatment during or after treatment.
2. Patients with uncontrolled systemic diseases (e.g., diabetes mellitus, heart diseases, liver diseases).
3. Patients with a history of head or neck radiotherapy.
4. Patients on chronic medication (e.g., steroids, antidepressants).
5. Smokers.
6. Patients without radiographs immediately after prosthetic loading.
7. Patients with psychiatric problems.
8. Patients with missing data on radiographic bone loss, mobility, prosthetic complications, or implant dimensions.
9. Patients with short implant designs.
10. Patients who lost implants before the 12-month follow-up.

Data Collection

The evaluations conducted during the patients' 12-month follow-up appointments were recorded and analyzed. The parameters assessed during these appointments include:

A. Demographic Data

1. Age of the patient.
2. Gender of the patient (Male/Female).
3. Education level (Primary School, Secondary School, High School, Undergraduate, Graduate).

B. Clinical Parameters

1. Tooth brushing habits (None, Once daily, Twice daily, More than twice daily).
2. Presence of functional pain (Yes/No).
3. Mobility (Yes/No).
4. Presence of exudate (Yes/No).
5. Attached gingiva (≥ 3 mm) (Yes/No).
6. Reason for tooth extraction (Endodontic, Periodontal, Other).
7. Immediate implant placement after extraction (Yes/No).
8. Implant diameter (Narrow < 3.75 mm, Standard ≥ 3.75 mm and < 5 mm, Wide ≥ 5 mm).
9. Implant length (Short implants excluded; Standard ≥ 10 mm).
10. Implant type by tissue relationship (Bone Level, Tissue Level).
11. Anatomical location of the implant (Maxillary Anterior/Posterior, Mandibular Anterior/Posterior).
12. Type of abutment (Standard, Screw-Retained, Ti-Base).
13. Status of the opposing arch (Natural Tooth, Tooth-Supported Fixed Prosthesis, Implant-Supported Fixed Prosthesis, Implant-Supported Removable Prosthesis, Tooth-Supported Removable Partial Prosthesis/Full Denture).
14. Occlusal table dimensions (Normal/Reduced by 30-40%).
15. Superstructure material (Metal-Ceramic, Monolithic Zirconia, Monolithic Glass Ceramic).
16. Presence and history of screw loosening (Yes/No).
17. Presence and history of cementation loss (Yes/No).
18. Framework-ceramic separation (Chipping) (Yes/No).

Data Evaluation

Evaluation of Implant Success and Survival

The success and survival of the implants were evaluated based on the 2007 consensus criteria established by the International Congress of Oral Implantologists (ICOI). The data were categorized

into four groups: Healthy-Successful, Sufficient Survival, Compromised Survival, and Unhealthy-Failed.

Evaluation of Radiographic Bone Loss

Digital radiographs (periapical and panoramic films) taken at the end of prosthetic treatment and during the 12-month follow-up were analyzed using Planmeca Romexis® software (Planmeca, Helsinki, Finland). Marginal bone loss was measured using ImageJ software (ImageJ 1.54g, NIH, USA). Measurements were calibrated based on the actual implant length. The mesial and distal marginal bone loss was calculated separately by subtracting the values obtained immediately after prosthetic loading from those at the 12-month follow-up.

Statistical Analysis

The collected data were analyzed using SPSS Statistics V.26 (IBM SPSS Statistics, USA). The normality of parameters was assessed using the Kolmogorov-Smirnov and Shapiro-Wilk tests. Descriptive statistical methods (mean, standard deviation, median, frequency) were employed. Quantitative data and intergroup comparisons were evaluated using the Kruskal-Wallis test, with Dunn's test for post hoc analysis. The Mann-Whitney U test was used for pairwise comparisons, and the Fisher-Freeman-Halton Exact Chi-Square test was employed for qualitative data comparisons. A significance level of $p<0.05$ was considered statistically significant.

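### The primary outcome data are worded as the effect of parameters nobody allocated, while every named test looks at one factor at a time and nothing limits the results to unadjusted associations

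*Combined protocol and SAP*

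**What the plan says.** The Outcome Measure Data entry, under the primary outcome of survival and complication rate, reads "The effect of prosthetic, anatomical and surgical parameters on implant survival rate and prosthetic complications". The test given for that outcome is "Method: Chi-Squared".

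The Statistical Analysis section adds that "Quantitative data and intergroup comparisons were evaluated using the Kruskal-Wallis test", with Dunn's test afterwards, Mann-Whitney for pairwise comparisons, and that "the Fisher-Freeman-Halton Exact Chi-Square test was employed for qualitative data comparisons". Otherwise it names only normality tests and descriptive statistics.

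On design, the Arm/Group Information entry says there are no study or control groups, and Volunteer Selection says that "Patients were selected from archives and evaluated during their 12-month follow-up appointments". The Clinical Parameters list records implant diameter, implant type, location (four levels), abutment (three levels), opposing arch, occlusal table and crown material (three levels) on the same patients.

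Bone loss is in the title, "Retrospective Evaluation of Prosthetic Complications and Peri-implant Bone Resorption in Implant-Supported Single Unit Fixed Restorations", but the text says only that quantitative data are compared between groups. It does not call those comparisons effects.

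**The concern.** An effect is a claim about what would change if the parameter were changed. In an archive series, the clinician chose the material, abutment and implant type, probably with the site in view. If one material is used mostly at posterior sites and posterior sites have more complications, a one-factor comparison of materials picks up the site difference. Dunn's test does not help, because it compares levels of the same factor.

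The plan names no regression, stratification, matching or covariate adjustment, and no sentence limits how the crude results are to be read. A report that follows it literally could tell clinicians that a material or abutment changes the complication rate when the analysis cannot separate that factor from where it was used. The same reading could carry over to bone loss.

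**Working it through.** The plan gives no figure on this point to reproduce. The only inputs from the documents are N = 100, the 5% level, d = 0.5 (from the sample-size paragraph) and the list of tests. Every risk, shift and split below is assumed, and the tested factor has no effect.

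**Complications, two-level factor, 50 v 50.** Let *p* be the posterior share in one group and 1 − *p* in the other, with risk *r1* at posterior and *r0* at anterior sites. The crude risks are

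x = p·r1 + (1 − p)·r0 and y = (1 − p)·r1 + p·r0.

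The crude odds ratio is [x/(1 − x)] / [y/(1 − y)]. Its log has standard error √(1/50x + 1/50(1 − x) + 1/50y + 1/50(1 − y)). The rejection rate is the exact sum of binomial probabilities over all tables with p<0.05.

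With r1 = 0.15 and r0 = 0.05, 10 events are expected:
- *p* = 0.7: x = 0.7 × 0.15 + 0.3 × 0.05 = 0.12, y = 0.08. Odds ratio (0.12/0.88)/(0.08/0.92) = 1.57, SE 0.68, interval 0.41 to 5.94.
- *p* = 0.8: x = 0.13, y = 0.07. Odds ratio 1.99, SE 0.70, interval 0.51 to 7.76.

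| Risks (posterior v anterior) | Test | 50/50 | 70/30 | 80/20 |
|---|---|---|---|---|
| 15% v 5% | Pearson | 5% | 10% | 17% |
| 15% v 5% | Fisher | 2% | 4% | 8% |
| 20% v 5% | Fisher | 2% | 8% | 17% |
| 30% v 10% | Pearson | 5% | 17% | 33% |

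Both tests are shown because the outcome entry says chi-squared and the Statistical Analysis section gives the exact version.

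**Bone loss, 0.5 SD shift by site, normal errors, simulated.**
- Two-level factor, Mann-Whitney: about 5% rejection when unrelated to site, 15–16% at 70/30 and 30–31% at 80/20. Repeat runs differ by about one percentage point.
- Three-level factor, such as material or abutment, Kruskal-Wallis, groups of 34/33/33: 5% when unrelated, 9% with posterior shares 70/50/30% and 16% with 80/50/20%.

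A linear model adjusted for site and implant type brings rejection back to about 5%. That must happen when site is the only confounder simulated, so it is not evidence that the model would remove confounding in the real data.

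**Cost of adjusting.** In a balanced two-level comparison, the correlation phi between factor and site is the difference in posterior shares: 0.7 − 0.3 = 0.4, or 0.8 − 0.2 = 0.6. The variance of the estimate rises by 1/(1 − phi²), which is 1/0.84 = 1.19 or 1/0.64 = 1.56. At N = 100, d = 0.5 and two-sided 5%, the noncentral *t* gives power 0.70 unadjusted, 0.62 at phi 0.4 and 0.51 at phi 0.6. This is before any gain from variance that the covariates explain.

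**The case against.** The strongest reply is that everything hangs on one noun in a results-template field. The title calls the study retrospective, the text says there are no separate groups, the Statistical Analysis section speaks only of comparisons, and no causal hypothesis is stated. That is fair, and it is why the core remedy is a change of wording. But the noun describes the primary outcome data, and nothing elsewhere qualifies it.

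A second reply is that the eligibility criteria already restrict confounding by excluding smokers, systemic disease, chronic medication and short implants. This stands in part. Those rules deal with some patient-level causes and one implant dimension. They leave site, implant type, abutment and material free to vary together.

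A third reply is that the larger two-level figures for bone loss (up to 31% at a 0.5 SD shift) do not describe the quoted outcomes. That is correct. They concern an outcome the plan never calls an effect and a two-level factor, whereas material and abutment have three levels and lower figures.

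A reader might also infer that with few events the complication tests are seldom misled. The documents do not support that reassurance: it holds for Fisher under one set of assumed risks, but not for Pearson under the same risks, nor for either test when the risks are higher.

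**Conclusion.** The point holds as a mismatch between wording and analysis: the plan promises effects and specifies only crude one-factor comparisons. It should be corrected, but it does not make the study unusable.

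The size is unknown. Under the assumed inputs, an inert factor shows a crude odds ratio for complications of about 1.6 to 2.0 and reaches p<0.05 in 10–17% of studies by Pearson or 4–8% by Fisher at 15% v 5%. By Pearson at 30% v 10%, the figure is 17–33%. These rates rest on 50 v 50 groups, a single confounder and splits of 70/30 or 80/20.

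Two stronger readings should be resisted. One is that confounding is present in these data or that a given result is false. No cross-tabulation or event count is provided, so the claim is only conditional. The other is that nothing about survival can be analysed. Exclusion criterion 10 removes patients whose implants were lost before follow-up, so implant loss cannot be modelled. The four ICOI categories still allow retained implants to differ in grade, and that reason does not apply to them.

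**What to change.** 1. In the Outcome Measure Data entry, replace the opening words *The effect of … on* with *The unadjusted association of … with*. Report every one-factor result of the Statistical Analysis section the same way, including those for ICOI category.

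2. For bone loss, name one or two main factors, for example material or abutment. For each, add a supportive linear model with robust standard errors, adjusted for a few recorded factors that precede it, such as site and implant type. Enter a three-level factor as two indicators with one joint test. State that the four locations are collapsed to anterior/posterior: a three-level factor plus site then needs 2 + 1 = 3 coefficients, against 2 + 3 = 5 uncollapsed, before implant type is added. Use one named bone-loss value, or fit mesial and distal separately and acknowledge the multiplicity. Call the result an adjusted association, and label it post hoc if the data have already been analysed.

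3. For complications, add a penalised logistic model with site only if the event count supports it, and state any collapsing of levels. Otherwise report crude associations with confidence intervals.

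The cost is wording plus one or two small models on data already collected. The adjusted bone-loss estimates will be less precise (power 0.70 falling to 0.62 or 0.51 in the cases above), and the study gives up statements about effects.

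### The required 80 patients does not follow from d = 0.5, alpha 0.05 and power 0.80 under any test the plan supports, and d is not the effect size for the primary outcome

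*Combined protocol and SAP*

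**What the plan says.** The only sample-size justification is in the Volunteer Selection section. It names the software and gives a significance level of 0.05, "an effect size (d) of 0.5" and power 0.80, and concludes that "at least 80 patients were required". It then adds 25% (20 patients) for dropout and data loss, which makes 100.

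Other sections bear on what that calculation could mean:

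- Arm/Group Information: "This study does not include any specific study or control groups".
- Outcome Measures: the primary outcome is "Implant survival and prosthetic complication rate", reported as a count of participants.
- Statistical Test of Hypothesis: "Method: Chi-Squared". The Statistical Analysis section instead gives the Fisher-Freeman-Halton test for qualitative data, with Kruskal-Wallis, Dunn and Mann-Whitney tests for quantitative data.
- Analysis Population Information: "Overall Number of Participants Analyzed: 100 participants".
- Exclusion Criteria, item 10: "Patients who lost implants before the 12-month follow-up".
- Data Collection: no factor is listed with more than five levels (education level and opposing arch have five each).

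**The concern.** Cohen's d is a standardised difference in means. It most naturally belongs to a comparison of two groups, and for that comparison 80 patients at d = 0.5 is a familiar mismatch. The plan also says that it has no groups, and its primary outcome is categorical. So there are two separate doubts: whether 80 follows from the stated inputs at all, and whether the calculation concerns the primary outcome.

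The 100 patients rest on this one sentence. The plan relates prosthetic, anatomical and surgical factors to survival and complications. A reader who meets a non-significant result may take the 80% power claim to mean that a moderate effect was unlikely to be missed. The sentence does not tell the reader which comparison, if any, has that power.

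**Working it through.** **Inputs from the Volunteer Selection section:** alpha 0.05, effect size 0.5 labelled d, power 0.80, required N 80. Test, sidedness, groups and outcome are not given, so each reading that the plan could support was tried.

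**1. The dropout step.** 80 × 1.25 = 100, which also equals 80/(1 − 0.20). This part is consistent.

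**2. Trying to reproduce 80.**

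Two equal groups of n, t-test: power is P(|T| > t critical), with T noncentral t on 2n − 2 degrees of freedom and noncentrality d√(n/2).
- Two-sided: n = 63 gives 0.795 and n = 64 gives 0.802, so the total is 128.
- One-sided: n = 50 gives 0.799 and n = 51 gives 0.806, so the total is 102.
- Mann-Whitney, efficiency 3/π = 0.955 for normal data: 64/0.955 = 67.02, so 68 per group and 136 in total; one-sided 51/0.955 = 53.4, so 54 per group and 108 in total.

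Paired or one-sample t-test, noncentrality d√n: two-sided N = 34. No such test is planned, and at N = 80 its power would be 0.993.

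A mislabelled 0.5:
- As ANOVA f (noncentrality N f²): 34, 42, 48 and 53 patients for two, three, four and five groups; 53 becomes 55 when balanced.
- As chi-squared w (noncentrality N w²): 32 (1 df), 39 (2 df), 44 (3 df), 48 (4 df), 70 (12 df). The four-category survival scale against a five-level factor has 3 × 4 = 12 df, the widest table that the listed categories imply. Splitting the last opposing-arch category makes six levels and 15 df, which gives 76.

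None of these is 80.

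**3. Power on the two-equal-group t-test reading, d = 0.5.**

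| Total N | Two-sided | One-sided |
|---|---|---|
| 100 (analysed) | 0.697 | 0.799 |
| 80 (stated minimum) | 0.598 | 0.716 |

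**4. What 100 patients can detect for complications.** The documents give no complication rates or group splits, so both are assumed here and varied. Power is the sum, over all pairs of event counts (a, b), of Bin(a; n₁, p₁) × Bin(b; n₂, p₂), counting only the pairs with two-sided Fisher p < 0.05. Rates giving about 80% power, with the exact power in brackets:

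| Lower rate | 50 v 50 | 80 v 20, lower rate in the 80 | 80 v 20, lower rate in the 20 |
|---|---|---|---|
| 5% | 5% v 27% (0.820) | 5% v 29% (0.806) | 34% v 5% (0.800) |
| 10% | 10% v 35% (0.820) | 10% v 39% (0.809) | 42% v 10% (0.815) |
| 20% | 20% v 48% (0.801) | 20% v 54% (0.809) | 54% v 20% (0.808) |
| 30% | 30% v 59% (0.801) | 30% v 66% (0.812) | 66% v 30% (0.816) |

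The detectable gap runs from 22 points (5% v 27%) to 36 points (30% v 66%), so a single example would mislead.

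**5. Marginal bone loss.** Two-sided Mann-Whitney, N = 100, normal data assumed, 100,000 simulations. At d = 0.5 power is 0.679 (50 + 50) and 0.485 (80 + 20). Power is about 0.80 at d = 0.58 (50 + 50, 0.797) and at d = 0.73 (80 + 20, 0.801).

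**The case against.** The strongest reply is that the sentence is incomplete rather than wrong. With no test named, the inputs do not fix any N. The stated figure is a floor, and a paired reading needing 34 would be met. Some settings do give 80: ANOVA with f = 0.4 and five groups; f = 0.5 with ten balanced groups; or 64 per group raised by 25%, since 64 × 1.25 = 80. The one-sided two-group figure of 102 is close to the final 100.

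Part of this stands. Because no test is named, one cannot say which input or output is in error. What can be said is that 80 does not follow under any test the plan supports. The near misses do not rescue it. The stated effect size is not 0.4, and no listed factor has ten levels. The plan presents 80 as a total and adds 25% afterwards, and it presents 100 as 80 plus an allowance for losses. A paired test is not planned, and 80 would not be its minimum.

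Two stronger readings are tempting, and the documents do not support either.

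- A reader might infer that the study is too small, or that 128 is the correct number. That needs a two-group, two-sided comparison of means at d = 0.5 to be the intended analysis, and the plan never says so.
- A reader might infer from exclusion criterion 10 that nothing can be said about implant survival. The criterion removes patients who lost implants before 12 months, so implant loss itself cannot be studied. It does not empty the four-category ICOI scale, which still grades retained implants.

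It is also fair to say that the data are already collected and that no estimate or p-value changes. That lowers the priority but does not make the claim correct.

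**Conclusion.** The point holds in this form: the stated 80 patients and 80% power are unsupported by the stated inputs, and the plan gives no power for its primary comparison, because d is not the effect size for a chi-squared or Fisher-Freeman-Halton test on counts.

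The size can be given only conditionally. If two equal groups, a t-test and d = 0.5 were meant, the 100 analysed patients have about 70% power two-sided or 80% one-sided. The power figures for complications rest on assumed rates and splits, and those for bone loss on roughly normal data. This should be fixed as a statement that is wrong as written. It does not call the analysis or the sample into question.

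**What to change.** Replace the sample-size sentence with the calculation actually run, giving test, sidedness, number of groups, outcome and the matching effect size. If no calculation supports 80, withdraw the claim that 80 patients give 80% power. Then state what 100 patients can detect, for example:

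> Prosthetic complications, two-group comparison, two-sided alpha 0.05, Fisher exact test, assumed rates: about 80% power with 50 v 50 patients for 5% v 27%, 10% v 35%, 20% v 48% or 30% v 59%. With 80 v 20 patients: lower rate in the 80, for 5% v 29%, 10% v 39%, 20% v 54% or 30% v 66%; lower rate in the 20, for 34% v 5%, 42% v 10%, 54% v 20% or 66% v 30%.
>
> Marginal bone loss, two-group comparison, two-sided Mann-Whitney test, alpha 0.05, roughly normal data assumed: 68% power for d = 0.5 with equal groups; about 80% for d = 0.58 (equal groups) or d = 0.73 (20:80).
>
> No power is claimed for implant loss, because patients who lost implants before 12 months are excluded. None was calculated for the four-category ICOI outcome or for factors with three or more levels.

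The cost is one rewritten paragraph. The stated power becomes less favourable and rests on declared assumptions. No extra patients and no change of analysis are needed.

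### Patients enter only with recorded 12-month outcomes, so non-attenders and decliners are never counted: the primary complication rate describes attenders, and the dropout part of the sample-size allowance does not fit the design

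*Combined protocol and SAP*

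**What the plan says.** All references are to the combined protocol and SAP.

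- **Sample size (Volunteer Selection).** The calculation ends with "0.80, at least 80 patients were required". The inflation, with its stated purpose, comes next in a sentence beginning "To account for potential dropout and data loss during follow-up, an additional 25% (20) patients were added, resulting in 100 patients at the start of".
- **Entry (Type of Units Assigned, Started).** "This study was conducted by including patients 12 months after delivery of the implant-supported restoration". The same entry says that recruitment closed once 100 patients had been reached, and the Completed entry also gives 100.
- **Selection and assessment (Volunteer Selection).** "Patients were selected from archives and evaluated during their 12-month follow-up appointments through clinical and radiographic examinations".
- **Eligibility.** Inclusion criterion 1 requires that 12 months have already passed since loading. Criterion 5 requires recorded data on bone loss, mobility and complications, and criterion 6 requires signed consent. Exclusion criterion 8 removes patients whose data on these outcomes are missing.
- **Outcome and analysis set.** The primary outcome includes the prosthetic complication rate, timed at 12 months after delivery. The Analysis Population section gives 100 participants analysed.
- **Losses after inclusion (Pre-assignment Details).** Some included participants were later removed because of missing, out-of-window, miscoded or unreadable records. No number is given.

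**The concern.** The allowance is written as if 100 patients were enrolled at loading and some would be lost on the way to month 12. The entry rules describe something else: the 12 months are over before a patient can qualify, and recorded 12-month outcomes are a condition of entry. Losses through non-attendance or refusal therefore fall outside the study and appear in no denominator.

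What is at stake is the meaning of a primary outcome. A rate timed from delivery of the restoration, with 100 entered, 100 completed and 100 analysed, can be taken for the rate among treated patients. Attendance may depend on the outcome. A patient with a loose or chipped crown may be more likely to come back, or may have had it repaired elsewhere. The bias could go either way, and nothing planned would let a reader judge its size.

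**Working it through.** **1. The plan's own figure.** 80 × 0.25 = 20 and 80 + 20 = 100. Equivalently, 80 / (1 − 0.20) = 100, so the inflation would tolerate a 20% loss and still leave 80. The step reproduces. The base of 80 is taken as given. Whether it follows from the stated effect size and power is a separate question and does not affect this point.

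**2. Where loss can occur.**

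| Stage | What the plan provides | Loss counted? |
|---|---|---|
| Crown delivered, 12 months pass | Not yet in the study | No |
| Patient does not attend at 12 months | Fails inclusion 5, meets exclusion 8 | No |
| Patient declines consent | Fails inclusion 6 | No |
| Record found unusable after inclusion | Pre-assignment Details | Described, no number |
| Included, completed, analysed | 100, 100, 100 | None shown |

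The dropout part of the allowance has no stage at which to act, because non-attendance makes a patient ineligible. The data-loss part does have one: records found unusable after inclusion. No section plans a count of eligible crowns, of non-attenders or of decliners, and none compares attenders with the rest.

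**3. Possible size (illustration only).** The documents give neither an attendance rate nor a complication rate. Assume one crown per patient, a rate p = 10% among 100 attenders, and a share m of otherwise eligible patients who did not attend. Decliners would be added in the same way.

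- Unseen patients behind 100 attenders = 100m / (1 − m)
- Lower bound (no non-attender had a complication) = p(1 − m)
- Upper bound (every non-attender had one) = p(1 − m) + m
- If non-attenders have k times the attenders' rate: p(1 − m) + m·k·p

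| Assumed m | Unseen | Lower | Upper | k = 0.5 | k = 2 |
|---|---|---|---|---|---|
| 10% | about 11 | 9% | 19% | 9.5% | 11% |
| 20% | 25 | 8% | 28% | 9.0% | 12% |
| 30% | about 43 | 7% | 37% | 8.5% | 13% |

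At m = 20%, for example: 0.10 × 0.80 = 8%, and 8% + 20% = 28%.

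**4. Outcome-dependent attendance, about 80% overall (assumed).** With 10 of 100 attenders having a complication, the rate among all is (10/a₁) / (10/a₁ + 90/a₀), where a₁ and a₀ are the attendance of patients with and without one.

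- a₁ = 95%, a₀ = 78%: 10.53 / (10.53 + 115.38) = 8.4%
- a₁ = 60%, a₀ = 83%: 16.67 / (16.67 + 108.43) = 13.3%

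**5. Against sampling error.** The exact 95% interval for 10/100 is 4.9% to 17.6%. Both values in step 4, every k = 0.5 and k = 2 value, and all the lower bounds lie inside it. Only the upper bounds (19%, 28%, 37%) lie outside.

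**The case against.** - **The allowance also names data loss.** This stands. Pre-assignment Details describes removal after inclusion for record problems, so that part has a purpose. A reader might infer that the whole allowance is void, but the documents support this only for its dropout part.
- **The order of events is not fully stated.** This also stands. Patients came from the archive and consented before taking part, and nowhere is consent said to have been taken at the 12-month visit. A reader might infer that entry and assessment are one visit and that nobody can be lost afterwards; the text does not establish that. The conclusion does not need it, because someone selected earlier who then failed to attend would lack the required outcomes and be ineligible.
- **No attendance rate is given.** Correct. A reader might turn the 20% tolerance into an attendance rate and infer that about 125 crowns lay behind the 100 patients. The 20% is a sample-size inflation for dropout and data loss together, and says nothing about attendance.
- **Moderate differential attendance stays within sampling error.** True under the assumptions in step 4. But the interval covers chance variation only, and selection uncertainty adds to it.
- **The restriction is partly disclosed.** Baseline Characteristics says the data come only from participants at the end of the 12 months. What is missing is a count and a stated limit on the conclusion.
- **This overlaps with complete-case selection.** In part: a non-attender is removed by the same criteria. The difference is that these patients may have complete delivery records and a surviving implant.
- **The planned chi-squared comparisons are not addressed.** Also true. The bounds above concern the overall rate only.

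**Conclusion.** The point holds. As written, the plan yields a complication rate for consenting attenders with complete data and counts nobody who was eligible but did not attend or declined. Its bias relative to all treated patients is of unknown direction. The dropout part of the allowance does not fit entry at 12 months; the data-loss part can stand.

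The size is not known. The ranges of 9–19%, 8–28% and 7–37% rest on an assumed 10% rate and on assumed non-attendance of 10%, 20% and 30%. They show what the missing denominator could hide and do not estimate a bias. A reader might go further and infer that the rate is materially wrong, but the documents do not support that, and the milder scenarios move it only a few points. The finding limits what the study can conclude; it does not invalidate the data collected.

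**What to change.** 1. **Volunteer Selection.** Reword the allowance as covering records found unusable after inclusion, and reconcile it with entry at 12 months. State the order of archive selection, consent and visit.
2. **Outcome Measures.** Define the primary rate, and limit the conclusion, to patients attending the 12-month visit with complete data.
3. **Patient flow.** From the archive used for selection, report how many otherwise eligible single-unit crowns reached 12 months, and how many patients attended, did not attend or declined. Add a sensitivity range that counts non-attenders first as all without and then as all with a complication.
4. **Fallback.** If the counts cannot be recovered, or only in part, say so and keep the restricted conclusion.

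The cost is a wording change, a modest archive count and two extra lines of analysis, with no additional patients or visits. The count may be only partly recoverable: the document mentions a time frame but gives no dates, and does not say that missed visits or refusals were logged. The other downside is a less favourable statement of how certain the rate is.
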